5.4 Drug administration

5.4.1 Venetoclax administration

a. Dosage Form

Venetoclax (GDC-0199/ABT-0199) is manufactured by AbbVie, Inc. and will be supplied by Abbvie as oral film-coated tablets of 10-mg, 50-mg, and 100-mg strength. Venetoclax tablets will be packaged in high-density polyethylene (PE) plastic bottles to accommodate the study design.

Venetoclax is an investigational agent supplied to investigators of this study by Abbvie Inc at no cost.

Each bottle of venetoclax tablets will be labelled in accordance with current International Conference on Harmonisation (ICH) Good Clinical Practice (GCP), FDA and specific national requirements.

Sites must request study drug by submitting an order form directly to the drug depot in order for the study drug to be shipped to the site pharmacy. The Investigator (or designee) will verify and acknowledge receipt of all study drug shipments by signing and returning all required forms.

The Investigational medicinal product should not be used for any purpose outside the scope of this protocol, nor can Investigational medicinal product be transferred or licensed to any party not participating in the clinical study. Venetoclax's data for Investigational medicinal product are confidential and proprietary and shall be maintained as such by the Investigators.

b. Drug Storage

Venetoclax must be stored at 15°C – 25°C (59°F – 77°F) in a locked and secured area with restricted access. The tablets should not be stored at freezer temperatures or allowed to freeze. All medication must be stored in a secure area under the proper storage requirements with access restricted to the site staff pharmacist or designee(s).

c. Accountability and Destruction of Investigational Medicinal Product

The Principal Investigator (or an authorized designee) at each participating institution must maintain a careful record of the inventory of the Investigational medicinal product received using the Drug Accountability Form. The study drug will be destroyed as per the institutions destruction policies and documentation of study drug destruction will be provided to Abbvie Inc. Both used and unused study drug may be returned to Abbvie Inc if requested.

For information on the formulation and handling of venetoclax, see the Venetoclax IB.

5.4.2 Quizartinib administration

a. Description

The chemical name of the investigational product, quizartinib, is N-(5-tert-Butyl-isoxazol-3-yl)-N'-[4-[7-(2-morpholin-4-yl-ethoxy)imidazo[2,1-b][1,3]benzothiazol-2-yl]phenyl] urea dihydrochloride salt.

Quizartinib is supplied as tablets each containing 15 mg, 20 mg or 30 mg quizartinib. The tablets also contain microcrystalline cellulose, magnesium stearate, and Opadry® II 85F18422 white film coating. They are packaged in high density polyethylene bottles, each containing 30 tablets, with child-resistant caps.

c. Potential Indications and Usage

**Quizartinib + Chemotherapy: Ongoing Clinical Trial
(ClinicalTrials.gov 10/26/17)**

ID	Setting	Phase	Clinical Trials	Identifier
AC220-A-U302	Frontline	Phase 3	Quizartinib + standard chemotherapy (Quantum-First)	NCT02668653
AC220-A-J102	Frontline	Phase 1	Quizartinib + 7 + 3 (in Japan)	NCT02834390
2012-1047	Both	Phase 1/2	Quizartinib + LDAC or AZA	NCT01892371
AML005	Both	Phase 2	Quizartinib and Omacetaxine	NCT03135054
AC220-007	Relapsed	Phase 3	Quizartinib versus LDAC, or MEC or FLAG-IDA (Quantum-R)	NCT02039726

d. Dosing

Each patient will receive or be instructed to take quizartinib oral tablets at the assigned dose once a day on in the morning for 28 consecutive days as 1 cycle of treatment.

e. Selection and Timing of Dose

Each treatment cycle consists of 28 consecutive days. Quizartinib will be taken orally once a day in the morning.

f. Packaging and Labeling

Please refer to the Investigational Brochure for packaging and labeling information.

5.4.3 Disposition of unused drug

All unused drug will be disposed of per institutional guidelines and procedures.

Rationale: Moderate CYP3A4 inhibitors have been safely administered with venetoclax with appropriate dose reduction as per US label. Moderate CYP3A4 inhibitors have been safely administered with Quizartinib.

Based on this we are allowing moderate CYP3A4 inhibitors on protocol

Assigned Venetoclax Dose	Venetoclax Dose Moderate CYP3A4 inhibitors
100mg	50mg
200mg	100mg
400mg	200mg

Strong CYP3A inducers – avasimibe, carbamazepine (Tegretol®), enzalutamide, mitotane, phenytoin (Dilantin®), rifampin (Rifadin®), St. John's wort

Moderate CYP3A inducers – bosentan, efavirenz, etravirine, modafinil, naftilin

Strong CYP3A inhibitors – Boceprevir, clarithromycin, cobicistat, conivaptan, danoprevir/ritonavir, elvitegravir/ritonavir, idelalisib,* indinavir, itraconazole, ketoconazole, mibefradil, lopinavir/ritonavir, nefazodone, neflifavir, paritaprevir/ritonavir combinations, ritonavir,

posaconazole, saquinavir, telaprevir, telithromycin, tipranavir/ritonavir, troleandomycin, voriconazole

Moderate CYP3A inhibitors – Amprenavir, aprepitant, atazanavir, cimetidine, ciprofloxacin, clotrimazole, crizotinib,* cyclosporine,* darunavir/ritonavir, diltiazem†, dronedarone, erythromycin, fluconazole, fluvoxamine, fosamprenavir, imatinib,* isavuconazole, tofisopam, verapamil

* These are anticancer agents; excluded on study as per protocol.

† Moderate CYP3A inhibitor per venetoclax FDA USPI.

Note: This is not an exhaustive list. For an updated list, see the following link:

<http://www.fda.gov/Drugs/DevelopmentApprovalProcess/DevelopmentResources/DrugInteractionsLabeling/ucm093664.htm>

Table 3: Instructions for the use of concomitant medications and therapies

Category of Use	Medication	Comment on Use	Restriction on Use
Recommended	Prophylactic antibiotics, antifungal agents, and antiviral agents Antiemetic agents	Strongly encouraged According to standard of care at MDACC	None None
Allowed	Oral allopurinol or rasburicase	At investigators discretion	None
	Leukapheresis	According to standard of care at MDACC	Before induction 1 day 1 only
	Red blood cell transfusion	None	None
	Platelet transfusion	None	None
	White blood cell transfusion	At investigators discretion according to standard of care at MDACC	None
	Myeloid growth factors or	At investigators discretion according to standard of care at MDACC	None

		At investigators discretion according to standard of care at MDACC	None
	Any other medication for supportive care	At investigators discretion according to standard of care at MDACC	None

5.5.3 Use of Blood Products

During the administration of venetoclax, patients may receive red blood cell (RBC) or platelet transfusions, if clinically indicated, per institutional guidelines.

Myelosuppression is expected in patients with AML due to underlying disease, as well as due to therapies (such as venetoclax and sorafenib), or both. Most patients have neutropenia, thrombocytopenia, or both at study entry. Significant or life-threatening myelosuppression may be managed with growth factor support including G-CSF, GM-CSF and erythropoietin/darbepoetin/blood transfusion according to institutional standard of care, American Society of Clinical Oncology (ASCO) Practice Guidelines, and/or NCCN Practice Guidelines.

5.5.4 Tumor Lysis Prophylaxis

There is a potential for TLS in patients treated with venetoclax, especially in those with elevated pretreatment LDH levels, elevated leukocyte count, renal dysfunction, and dehydration. To mitigate the potential risk of TLS, patients will be required to have WBC count <10K prior to initiating venetoclax on C1D8 and will receive TLS prophylaxis prior to venetoclax initiation on C1D8 and prior to venetoclax dose escalation. Patients will be hospitalized on Day -1 (C1D7) of venetoclax through at least 24 hours post target cohort dose. Thus it is projected that if WBC is <10K on C1D7, patients will be hospitalized C1D7 (day -1 venetoclax) through C1D12 (24 hours post venetoclax dose escalation completed).

Venetoclax will be administered at a dose of 50 mg on day 8, 100 mg on day 9, 200 mg on day 10, and 400mg on days 11-28 of the first cycle. All subsequent cycles, Venetoclax will begin on Day 1. For toxicities that could be attributed to either drug, Venetoclax or Quizartinib or both could be held or modified, based on perceived contribution (as per treating physician, in discussion with PI) of respective drug to the toxicity. This schedule may need to be adjusted if we see any signs of TLS. If this occurs it should be discussed with the PI and the new schedule documented in the patients chart.

To mitigate the risk for TLS, subjects must be receiving tumor lysis prophylaxis, including hydration (oral, intravenous) and treatment with a

uric acid reducing agent (allopurinol, rasburicase) at least 24 hours prior to the first dose of venetoclax and during the venetoclax ramp up period of Cycle 1.

TLS chemistry tests (potassium, uric acid, creatinine, calcium and phosphorus) will be obtained prior to dosing and 6-8 hours after each day of a new venetoclax dose. TLS chemistry test results will be reviewed by the investigator in real time and prior to the subject's next dose to ensure appropriate management. If a subject meets criteria for clinically significant laboratory or clinical TLS, no additional venetoclax should be administered until resolution.

Venetoclax interruption for up to 72 hours following transient (< 48 hours) chemical changes and laboratory TLS will be allowed and will not require a dose reduction.

5.5.5 Prohibited Food

Use of the following foods is prohibited during the study and for at least 7 days prior to initiation of study treatment:
Grapefruit, grapefruit products, Seville oranges (including marmalade containing Seville oranges) or starfruit within 3 days prior to the initiation of study treatment

Patients who consume any of these foods will be discontinued from study treatment and followed for safety outcomes for 4 weeks after the last dose of study treatment or until initiation of another subsequent anti-cancer therapy, whichever comes first.

5.5.6 P-glycoprotein substrates

There is a narrow therapeutic index for interactions between venetoclax and P-glycoprotein substrates. A list of p-glycoprotein substrates is provided via link below. Patients who are taking a p-glycoprotein substrate and venetoclax should take the p-glycoprotein substrate 6 hours before the venetoclax.

<http://www.fda.gov/Drugs/DevelopmentApprovalProcess/DevelopmentResources/DrugInteractionsLabeling/ucm080499.htm>

Note: Every effort will be made to adhere to the quizartinib and venetoclax dose reduction. Variations in schedule of events such as late/missed interventions that do not affect the rights and safety of the patient will not be considered as deviations.

5.5.7 DRUG DRUG INTERACTION ASSESSMENT

Both quizartinib and venetoclax are CYP3A and Pgp substrates. Both quizartinib and venetoclax are Pgp inhibitors, and the latter also inhibits BCRP. Therefore, the potential for a two way drug drug interaction will be assessed in a substudy of the first 12 subjects enrolled in the Phase 1b. Specifically this substudy will assess the effect of venetoclax on quizartinib PK (i.e. Cmax and AUC0-24h) and the effect of quizartinib on venetoclax PK (i.e. Cmax and AUC0-24h) as summarized in section 5.1.

6.0 CORRELATIVE/SPECIAL STUDIES (Optional)

Biomarker assessments may include:

6.1 81-gene sequencing in all patients

As a standard of care all AML patients at MDACC are evaluated for karyotype and molecular mutation profile using a CLIA-certified next-generation 81-gene panel sequencing platform. The effects of the combination will be compared not only to historical outcomes in matched groups of patients, but also at the molecular and cellular level by correlating with karyotype and molecular mutation profile. The 28-gene panel will be performed on the screening BM aspirate and the progression BM aspirate.

6.2 Minimal Residual Disease assessment by flow-cytometry

As a standard of care all BM aspirates including but not limited to the screening BM, end of cycle 1 BM, end of cycle 3 BM, will be evaluated for MRD by validated 17-color multiplanar flow-cytometry at MDACC.

6.3 Gene expression signatures by RNA sequencing and/or RT-PCR

This will be performed on the pretreatment BM aspirate and when available, the progression/relapse BM aspirate.

6.4 Cytof analysis

We will analyze BCL-2 family expression, stem cell surface markers and intracellular signaling markers in AML cells by CyTOF (mass cytometry) assay established in [name] laboratory. This will be done on mononuclear cells obtained from BM aspirate and when available from PB at all time points specified in 7.1.8 and 7.2.9.

6.5 Immune assays

To analyze immune modulation including alterations in total and percent of CD3+ T-cells, total and percent of various T-cell subsets (Cd4-effector, CD4-reg, CD8 cytotoxic T-cells), and total and percent of T-cell/T-cell subsets expressing specific checkpoint receptors/ligands with single-agent quizartinib and with the combination. This will be done on peripheral blood and BM aspirate at all time points specified in 7.1.8 and 7.2.9.

6.6 BH3 profiling of BCL-2 family member dependency

BH3 profiling will be performed on PB samples at pre-treatment, pre venetoclax dose 1 (cycle 1 day 7), and at progression.

6.7 Single Cell Genotyping

To precisely monitor mutant clones and address clonal heterogeneity on a single cell level, we will utilize a high-throughput **single-cell genomics platform** for targeted sequencing, in collaboration with [name] (UCSF) on PB at all time-points in 7.1.8 and 7.2.9

7.0 PATIENT EVALUATION

Every effort will be made to adhere to the schedule of events and all protocol requirements. Variations in schedule of events and other protocol requirements that do not affect the rights and safety of the patient will not be considered as deviations. Such variations may include laboratory assessments completed outside of schedule, occasional missed required research samples such correlative assays.

7.1 Pre-Treatment Evaluation

All pretreatment studies should be obtained within 14 days from time of first dose of the study drug administration, unless otherwise specified:

- 7.1.1 A complete history and physical, concomitant medications and performance status.
- 7.1.2 CBC, platelet count, hemoglobin, differential (differential can be omitted if WBC is $\leq 0.5 \times 10^9/L$).
- 7.1.3 Creatinine, total bilirubin, ALT, potassium, magnesium, calcium, sodium, chloride, $\text{CO}_2(\text{HCO}_3)$, uric acid, phosphorus, and BUN.
- 7.1.4 Serum or urine pregnancy test in females of childbearing potential, should be performed within 72 hours before the initiation of therapy.
- 7.1.5 Bone marrow aspirate with or without biopsy within the last 21 days preceding study initiation.
- 7.1.6 Evaluation of FLT3, NPM1, IDH1 & 2 should have been done within 60 days preceding study initiation.
- 7.1.7 12-lead EKG (in triplicate) and ECHO and/or MUGA.
- 7.1.8 Pretreatment optional correlative studies (see section 6.0)

Peripheral blood (up to 40 cc) – (1) Cytof and gene expression signatures by RNA sequencing and/or RT-PCR, (2) BH3 profiling, (3) immune panel in the blood prior to first dose of quizartinib at baseline (Cycle 1 Day 1)

- Bone marrow samples (up to 15 cc): (1) Mutation analysis of leukemia associated genes by deep sequencing; (2) Cytof (3) immune panel prior to first dose of quizartinib at baseline (Cycle 1 Day 1)

7.2 Evaluation During Treatment

- 7.2.1 During Cycle 1 Day 7-12 patients will be admitted to the inpatient service and have labs done at least daily to monitor closely for TLS, proliferative disease, and electrolyte changes. Patient can be treated as an outpatient if WBC $< 10,000$ with approval from the PI.

- 7.2.2 Physical exam on day 1 of each cycle (± 1 days) for the first 4 cycles.
- 7.2.3 CBC, platelet count, hemoglobin, differential at least twice weekly for the first 3 cycles, then at least once a week (differential can be omitted if WBC is $\leq 0.5 \times 10^9/L$). Outside labs may be used, but the PI/Treating physician must review all protocol specific outside lab results and determine the clinical significance of abnormal values then sign/date the results or dictate this process in the medical record.
- 7.2.4 Creatinine, total bilirubin, ALT, K, Mg, Ca, sodium, chloride, and CO₂ (HCO₃) on day 1 prior to start of quizartinib, at least twice weekly for the first 3 cycles, then at least once a week. For initial labs and initial management of electrolyte imbalances and prevention of tumor lysis syndrome patients will be admitted and monitored inpatient for cycle 1 Days 7-12 (section 5.5.4).
- 7.2.5 Laboratory tests can be ordered more frequently if mandated by development of peripheral blast/blood counts or electrolyte/liver function test abnormalities.
- 7.2.6 Bone marrow aspiration for differential and PCR for FLT3 on day 28 (± 7 days) of cycle 1, day 28 of cycle 3 (± 7 days), then every 2 cycles. Bone marrow tests can be ordered more frequently if mandated by development of peripheral blood counts. No repeat bone marrow is necessary if nonresponse or progressive disease can be unequivocally diagnosed from peripheral blood tests or, in patients with a WBC < 0.3 if the bone marrow test is considered noncontributory by the investigator at any time point.
- 7.2.7 Concomitant medication data will not be collected or entered into the case report form (Prometheus is the case report form for this study). Concomitant medication data will not be collected or entered into the case report form except for concomitant hydroxyurea if administered during the first cycle; however, the subject's medication record will contain a list of concomitant medications.
- 7.2.8 EKG will be performed on day 1, day 5, day 8, and day 12 of the first cycle (all ± 2 days) Day 1 and day 8 ECG are collected pre-dose; day 5 are collected pre-dose and 4 hrs (+/- 2 hrs) post-dose; day 12 are collected 4 hrs (+/- 2 hrs) post-dose. Then ECG to be done on day 1 of each cycle for cycles 2, 3, 4 and 5 before initiation of quizartinib and 4 hr (+/- 2 hrs) post dose, then pre-dose every 2 subsequent cycles. EKG may be omitted if patient has not received study drug (quizartinib) in the 48 hrs preceding the time when EKG is done. EKG at screening and for the first 3 cycles will be done in triplicate. Subjects **should rest in the supine position or semi-recumbent, with the same position used for an individual subject for the duration of the study, for at least 5 minutes before each 12-lead ECG recording is started. The ECGs should be reviewed, signed,**

and dated by a qualified physician (or qualified physician's assistant or nurse practitioner) and any clinically important finding recorded on the appropriate eCRF. The results will include heart rate, PR interval, QRS interval, QT interval, and QTcF interval. QTcF is calculated using the formula, $(QT)/3\sqrt{RR}$. All screening and on study ECGs should be obtained in triplicate (10 seconds for each ECG over the 5-minute period).

- A. On patients who increase the dose of Quizartinib or start therapy with a drug that is a moderate CYP3A4 inhibitor, an EKG will be required 24 hrs (± 6 hrs), 7 days (± 2 days) and 14 days (± 2 days) after the dose increase or after the start of the moderate CYP3A4 inhibitor.
- B. Patients who had their dose reduced because of QTc prolongation and have their dose re-escalated as described in section 5.2.3 will have an EKG repeated 24 hrs (± 6 hrs) and 7 days (± 2 days) after re-escalation.
- C. The QTc interval will be calculated by Fridericia's correction factor (QTcF). The 12-lead EKG evaluation will consist of 3 separate EKGs obtained at least 5 minutes apart.

7.2.9 Peripheral blood (up to 40 cc each time) and bone marrow (up to 15 cc each time) for pharmacodynamic studies (Optional) as defined in section 6.0 on

Peripheral blood:

- Prior to first dose of quizartinib at baseline (Cycle 1 Day 1).
- Cycle 1 Day 8: prior to the first dose of venetoclax
- Cycle 1 Day 15: prior to the dose of quizartinib and venetoclax (steady state)
- Cycle 1 Day 28 (+/- 4 days): prior to the dose of quizartinib and venetoclax
- At progression/relapse (if sample available)

Bone marrow samples:

- At screening (within 14 days preceding study initiation) as per section 7.1.8 – This BM will be done after the patient is consented to the study
- Cycle 1 day 8 (prior to the first dose of venetoclax)
- At the time of disease assessment on day 28 (+/- 4 days)
- At response assessment pre-cycle 4 (EOC 3)
- At progression/relapse (if sample available)
- Missed samples or cycles outside the provided time windows for correlative studies and/or for PK analysis will not constitute

protocol deviations. These studies are optional on this protocol.

7.2.10 All treatment prescriptions for quizartinib and venetoclax must be written by the patient's attending physician at MDACC or the PI of the study. We do not intend for the subjects to receive prescriptions for quizartinib or venetoclax at an outside physician's office. During the first cycle all the protocol required laboratory evaluations will be done at MDACC. Subsequently, the patient may have the laboratory work done at a local clinic and the results reported to the research nurse for the study. The laboratory work done at the local clinic will be forwarded to the patient's attending physician at MDACC or PI of the study, who will sign off on the labs to verify that the results have been reviewed.

Outside Physician Participation During Treatment

1. MDACC Physician communications with the outside physician is required prior to the patient returning to the local physician. This will be documented in the patient record.
2. A letter to the local physician outlining the patient's participation in a clinical trial will request local physician agreement to supervise the patient's care.
3. Protocol required evaluations outside MDACC will be documented by telephone, fax or e-mail. The PI/treating physician must review the labs, determine clinical significance and sign and date the report.
4. A copy of the informed consent, protocol abstract, treatment schema and evaluation during treatment will be provided to the local physician.
5. Documentation to be provided by the local physician will include progress notes, reports of protocol required laboratory and diagnostic studies and documentation of any hospitalizations.
6. The home physician will be requested to report to the MDACC physician investigator all life threatening events within 24 hours of documented occurrence.
7. All follow-up visits that correspond with drug dispensation will be performed at MDACC.
8. Changes in drug dose and/or schedule must be discussed with and approved by the MDACC physician investigator, or their representative prior to initiation, and will be documented in the patient record.

7.2.11 For patients that remain on study with no significant toxicity for more than 6 months, subsequent evaluations during study may be modified after discussion with the PI. These include a decrease in frequency of bone marrow aspirations to every 6-12 months (or as clinically indicated) and other laboratory tests to once every cycle.

7.2.12 Pregnancy test (urine or serum) in females of childbearing potential every 3 months (\pm 2 weeks).

7.2.13 Patients will be followed for survival at MD Anderson Cancer Center (MDACC) every 3 to 6 months after the end of treatment visit for up to 5 years after completion of active treatment. If the patient is unable to return to MDACC the follow-up visits may be conducted via telephone.

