3.1 General

The study will be a phase Ib/II, single-institution, open label, non-randomized, single arm, clinical trial. All patients will be registered through CORe/PDMS.

• Phase Ib

- This will include FLT3-ITD mutated patients with relapsed/refractory AML (up to four prior therapeutic regimens for AML i.e. up to salvage 4 status), including patients who may have been previously exposed to one prior FLT3-inhibitor other than quizartinib. Relapsed/ refractory status defined by the failure of at least one prior cycle of therapy for active AML (including but not limited to cytotoxic chemotherapy, hypomethylator therapy, immune-based therapy, stem cell transplant or stem cell therapy,

- one prior FLT3-inhibitor therapy exposure allowed, investigational therapy, and others).
- The DLT assessment period will be only during Cycle 1 of the Phase Ib (DLT assessment period = 28 days).

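### At quizartinib 30 mg only one scheduled ECG (Day 12) follows venetoclax start within the 28-day DLT window, so a QTc DLT that first arises later could go uncounted

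*Combined protocol and SAP*

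**What the plan says.** - **DLT window.** Section 3.1: "The DLT assessment period will be only during Cycle 1 of the Phase Ib", set at 28 days. Section 3.3 clears a level when fewer than 2 of 6 patients have a DLT in that time. Section 11.2 monitors phase II toxicity as DLTs within one cycle.
- **ECGs in cycle 1.** Section 7.2.8: "EKG will be performed on day 1, day 5, day 8, and day 12 of the first cycle", each with a 2-day tolerance. "Day 1 and day 8 ECG are collected pre-dose", while "day 12 are collected 4 hrs (+/- 2 hrs) post-dose". After that, "Then ECG to be done on day 1 of each cycle for cycles 2, 3, 4 and 5". Section 5.1.1.1 bars phase Ib patients from starting cycle 2 before 28 days.
- **Extra ECGs.** Section 7.2.8A adds recordings at 24 hours, 7 days and 14 days. They apply to "On patients who increase the dose of Quizartinib or start therapy with a drug that is a moderate CYP3A4 inhibitor". Starting venetoclax is not a trigger.
- **Dosing.** Venetoclax starts on Day 8 (section 5.1) and is given at "400mg on days 11-28 of the first cycle" (section 5.5.4). Level 0 stays at quizartinib 30 mg. Level +1 starts at 30 mg and may go to 60 mg on Day 12 if the Day 12 QTcF is below 450 msec.
- **QTc DLT.** Section 3.4 requires QTcF above 500 msec, confirmed by triplicate ECG.
- **Interaction.** Section 5.5.7 plans to assess a possible two-way interaction in the first 12 patients.

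**The concern.** This DLT is found by recording an ECG. Section 2.2 describes the Grade 3 cases in the first-in-human quizartinib study as asymptomatic, so symptoms cannot be relied on to prompt an unscheduled recording. The closer monitoring in section 5.2.2 (Table 2) and section 10.4.1 begins only once prolongation has been seen.

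The combination is the new element of this trial, and at level 0 its QTc effect is looked at once in the window, one day after venetoclax reaches 400 mg. If prolongation first appears later, it is not counted and the 2-of-6 rule is more likely to clear level 0. If 30 mg becomes the RP2D, the phase II toxicity boundary in Table 5 inherits the same gap.

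**Working it through.** The documents give no operating characteristics for the phase Ib rule and no ECG detection rate, so there is no stated figure to reproduce for this point. For phase II, the boundaries in Tables 4 and 5 and five Table 6 entries that were checked do reproduce (for example 0.1605). Those figures treat every DLT as observed.

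**1. Nominal ECGs after the first venetoclax dose, up to Day 28**

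| Patient | ECG days | Count |
|---|---|---|
| Level 0 | 12 | 1 |
| Level 0, starting a moderate CYP3A4 inhibitor | 12, plus three from that start | up to 4 |
| Level +1, step-up on Day 12 | 12, 13, 19, 26 | 4 |
| Level +1, no step-up | 12 | 1 |

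At level 0, Days 13-28 (28 − 12 = 16 days) have no scheduled ECG. Of the 18 days at venetoclax 400 mg (Days 11-28), only Day 12 has one. With the 2-day tolerance, a Day 12 ECG taken on Day 10 would precede 400 mg altogether, and a Day 8 ECG taken late could follow venetoclax start.

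**2. Exposure at Day 12**

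The fraction of steady state after 12 daily doses is 1 − r^12. Section 2.2 supplies the inputs.
- Half-life of about 100 hours: r = 2^(−24/100), giving 0.86.
- Quizartinib accumulation ratio 5.7: r = 1 − 1/5.7, giving 0.90.
- AC886 accumulation ratio 8.2: r = 1 − 1/8.2, giving 0.79.

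Quizartinib is thus close to steady state on Day 12, but only two venetoclax doses at 400 mg have been given.

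**3. Effect on the 2-of-6 rule**

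Let p be the true DLT rate and s the share of DLTs detected (assumed). With q = p × s, P(at most 1 of 6) = (1 − q)^6 + 6q(1 − q)^5.

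| p | s = 1 | s = 0.5 |
|---|---|---|
| 5% | 0.967 | 0.991 |
| 10% | 0.886 | 0.967 |
| 20% | 0.655 | 0.886 |
| 30% | 0.420 | 0.776 |

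Applying s to the whole rate assumes that every DLT is a late QTc event. At p = 30%, the result is 0.487 for s = 0.9 and 0.954 for s = 0.2.

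**4. Illustration of s**

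Assume persistent prolongation with onset uniform over Days 9-28 (20 days). Level 0 catches onsets on Days 9-12, so 4/20 = 20%. A stepped-up level +1 patient is covered through Day 26, so 18/20 = 90%. If the Cycle 2 Day 1 pre-dose ECG also counts, both reach 20/20. If onset is by Day 8 and persistent, both are already at 100% without it.

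**The case against.** The count itself is not in dispute. What it implies can be contested on several grounds.

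- **Onset may be early.** Section 2.2 reports that QTcF above 500 msec appeared between 2 hours after the first dose and Cycle 1 Day 8. ECGs on Days 1, 5, 8 and 12 cover that period. This stands for quizartinib alone; those data do not address venetoclax added on Day 8.
- **The event may be rare.** Section 2.2 gives 5% above 500 msec at 30 mg as monotherapy. At that rate, half detection moves the clearing probability by about 2 points. This stands, but the rate on the combination is unknown.
- **The interaction may be small.** Section 2.5.3 says venetoclax does not inhibit CYP3A4 at clinically relevant concentrations, which leaves mainly the P-gp route raised in section 5.5.7. So an interaction is an open question in the protocol, not an expected effect.
- **The level +1 ECGs are not surplus.** They follow a dose increase and are the only ECGs in the window at 60 mg after the step-up. A reader might infer that all level +1 patients are watched more closely. The documents do not say so: patients who do not step up get none of the three, and level 0 patients who start a moderate CYP3A4 inhibitor get the same three.
- **Other safeguards exist.** Cycle 2 Day 1 has pre- and post-dose ECGs, section 10.4.1 requires Grade 3 or higher prolongation to be recorded whatever its cause, and the RP2D may be set below the MTD. Persistent prolongation on Day 29 could therefore inform the RP2D. It would still not count in the 28-day rule, and section 11.3 ties the toxicity summary to completion of 28 days.
- **Phase II differs slightly.** Section 5.1.1.1 lets patients with active disease start a cycle from Day 21, so for some the next ECG would come sooner.

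**Conclusion.** The point holds as a gap in ascertainment. On the nominal schedule, level 0 has one ECG on the combination within the DLT window, against four for level +1 patients who step up on Day 12. For the same pattern of events, detection at level 0 cannot exceed detection in those patients, so any bias favours clearing level 0. It would carry into phase II DLT monitoring if the RP2D is 30 mg.

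A reader might infer that QTc DLTs are in fact under-detected, or that the level 0 rate would be seen at some fixed fraction of its true value. The documents support neither. Nothing in them says what share of QTc DLTs on the combination arises after Day 12. The effect runs from none (early, persistent onset), through 0.97 to 0.99 (5% true rate, half detected), to 0.42 to 0.78 (30% true rate, all late QTc events, half detected). The last two rest on assumed detection shares, and the 30% case also on an assumed mix of events.

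The ECG schedule and the 28-day window do not contradict each other, but they have not been matched. Because the remedy is almost free, it is worth making.

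**What to change.** Reconcile sections 7.2.8 and 7.2.8A with the DLT window in sections 3.1, 3.3 and 3.4. State that the already scheduled Cycle 2 Day 1 pre-dose ECG counts towards cycle 1 DLT ascertainment, at both dose levels and in phase II. Say how it is handled when cycle 2 is delayed, starts early (phase II) or does not start. Align the timing of the toxicity summaries in section 11.3.

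The cost is wording only, with no added procedure and no change to dosing. The DLT assessment closes about one day later, or more if cycle 2 is delayed. The change captures persistent prolongation only: a transient episode between Day 12 and Cycle 2 Day 1 would still be missed at level 0. That limit should be acknowledged when QTc DLT counts are compared between levels.
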